desired behaviors such as retention. CM, however, has not yet been tested or adapted for use in community-based programs for offender populations, particularly to encourage treatment admission and attendance.

The study will provide incentives to study participants for enrollment at the Walden House program and for attendance during the residential and the outpatient phases at Walden House. For a continuum of care model (such as that provided by CDCR), enrolling in community treatment is essential and increases the likelihood that clients will receive the benefits of treatment. In addition, increasing the amount of time that clients participate in residential and outpatient treatment is an important goal for improving outcomes. Only about 56% of clients referred from the SATF prison treatment programs to Walden House show up for admission, and the average length of attendance is 38 days. Increased enrollment would mean that a larger percentage of participants from prison-based treatment would be exposed to continuing treatment in the community, thereby improving the overall efficiency of CDCR's treatment system. Increased attendance would mean that clients have greater exposure to the treatment environment and treatment activities of the Walden House program, with the likelihood that this would improve post-treatment outcomes.

INTRODUCTION TO THE STUDY

The UCLA Integrated Substance Abuse Programs (ISAP), in collaboration with Walden House and the California Department of Corrections and Rehabilitation, is conducting a five-year health services research study that will involve a randomized test of the use of incentives to improve treatment utilization among parolees in community-based treatment. The incentives are in the form of vouchers that are redeemable for cash deposited into their Walden House bank account. The goals of the study are to increase the likelihood that prison treatment participants with a referral to community treatment will actually enroll in community treatment following release to parole and, once enrolled, will increase the amount of time that they participate in treatment. Increased exposure to community treatment as a result of incentives is expected to result in improved long-term outcomes of parolees who have participated in prison-based and community-based treatment.

The study has six specific aims:

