Reset – Unexcused absences result in incentives being reset to the Week 1 amount (Figure 3), beginning on the first Monday after the client returns to WH. Upon return from an unexcused absence, no incentives may be earned until reset begins the following Monday. Then, after you achieve 2 weeks of continuous attendance (10 days if residential; 6 days if outpatient), you go up to the next earning level, above the amount you were earning before your unexcused absence.

Outpatient attendance– 3 clinical contacts must be made per week. Any excused absence must be made up the following week by the client attending an extra clinical activity. No voucher will be received on an excused day. You will receive the voucher the following week at the amount you were scheduled to earn on the excused day. Missed days, even if excused, and make-up days will be reflected on the detailed weekly summary voucher. If a missed day is not made up the next week, then incentives will be reset.

Relapse - If you relapse but do not miss a scheduled treatment day (or session if you are an outpatient), then your earnings remain the same.

Late – In outpatient treatment, if you are no more than 15 minutes late and have a good explanation, you can be excused. If you are more than 15 minutes late, then you are in nonattendance and no voucher will be given for the day. Walden House staff may determine any exceptions.

Discharge – You are in the study for 22 weeks from the day you start earning money. You can only start earning money on a Monday. If you are discharged and then re-admitted 2 months later, you can continue earning as long as you remain within the 22 week window. After the 22 weeks are over, you cannot earn incentive vouchers.

HOW DOES A MISSED TREATMENT DAY AFFECT VOUCHER DELIVERY

If a client misses a treatment day, or even many weeks, no vouchers may be awarded on incomplete days or days that the client is physically absent from treatment (unless it is an excused absence). When the client returns he must begin the two week reset function of earning at the initial earning amount (\$2.50 per day) via reset vouchers. A client may only receive vouchers until the end of 22 weeks after he first began the study.

Reset in Residential Treatment

If the client was in residential treatment when he left, he must attend treatment for 10 treatment days (2 weeks) without missing a scheduled day, in order to regain his previous

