The UCLA Integrated Substance Abuse Programs (ISAP), in collaboration with Walden House and the California Department of Corrections and Rehabilitation, is proposing a five-year health services research study that will involve a randomized test of the use of incentives to improve treatment utilization among parolees in community-based treatment. The incentives are in the form of vouchers that are redeemable for goods or services. The goals of the study are, by using incentives in accordance with current CM principles and practices, to increase the likelihood that prison treatment participants with a referral to community treatment will actually enroll in community treatment following release to parole and, once enrolled, will increase the amount of time that they participate in treatment. Increased exposure to community treatment as a result of incentives is expected to result in improved long-term outcomes of parolees who have participated in prison-based and community-based treatment. Because treatment staff “buy in” will be important for the success of the intervention, staff will be included in the final development of the protocol, as well as in implementation of the main study. If the results are positive, the CM intervention would provide correctional treatment systems and treatment programs with an effective technique to promote attendance and participation in community treatment and thereby improve drug use, crime, and other outcomes.

The study has six specific aims:

- (1) Determine whether offering an incentive (voucher) increases admission to community treatment by parolees who have participated in prison treatment.
- (2) For parolees who enter community treatment, determine whether providing incentives for attendance results in greater retention in treatment.
- (3) For parolees who enter community treatment, determine whether providing an incentive increases the likelihood that clients will participate in HIV testing and counseling.
- (4) Assess the long-term impact of the use of incentives on drug use, crime, and psychosocial outcomes at 12 months following the end of the five-month intervention.
- (5) Assess the long-term impact of the use of incentives to promote treatment participation on HIV-risk behaviors at 12 months following the end of the five-month intervention.
- (6) Assess issues of acceptability, satisfaction, and sustainability of the use of incentives to increase admission and retention among staff and clients.

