To accomplish these aims, the study design includes two phases: the Admission Phase and the Attendance Phase. In the Admission Phase, consenting clients at the Substance Abuse Programs at the California Substance Abuse Treatment Facility will be randomly assigned to the Admission Incentive group or to the Admission Information group. Upon release to parole, those in the Admission Incentive group who enroll in the Walden House treatment program will receive the voucher. In the Attendance Phase, which will last for five months, parolee subjects who enroll in treatment will be asked if they wish to participate in the Attendance Phase; if so, they will be consented and randomized to the Attendance Incentive group or to the Attendance Information group. Those in the Attendance Incentive group will be provided vouchers for

attendance using an escalation/reset schedule. Twelve months after the end of the intervention (i.e., 17 months following release to parole), all study participants will be tracked for a follow-up interview. Administrative records will be obtained from Walden House and from criminal justice agencies. Qualitative data will be collected from records of meetings with Walden House staff and from focus groups with staff and clients.

HUMAN SUBJECTS

Proposed Involvement of Human Subjects

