The planned work schedule for the five-year project will be conducted in four main phases: (1) Start-up and Intervention Development, (2) Staffing and Training, (3) CM Implementation, and (4) Follow-up, Data Analyses, and Report Writing (see Table 3). The main activity for Phase 1 will be intervention development and piloting. This will include the development of a CM procedures Manual appropriate for residential treatment in the first half of Year 1, with input from the Intervention Development Workgroups consisting of treatment staff, clients, and research staff, aided by a technical writer. Instruments will be reviewed and revisions, additions, or deletions will be made. We will also secure IRB, OHRP, and CDCR approvals, obtain the Confidentiality Certificate, and create the data management system. Phase 2 involves selecting and training clinical and research staff, and setting up the research office at Walden House (the SATF research office already exists). Phase 3 involves CM study implementation. Recruitment will begin in the second half of Year 1. It will take about 25 months to enroll 250 participants into the study. Phase 4 will include the 18-month post-release assessment of clients, preliminary

and final data analysis, and report writing. Preparation of conference presentations and articles will commence in Year 3.

Table 3: Project Timeline

Phase/Activity	Months
Start-up & Intervention Development	
Information Session, Intervention Workgroup, manual development	1-3
Intervention piloting and manual revision, recruitment “pipeline” study	4-6
Finalize instruments, create data management system	1-5
Obtain IRB, OHRP, & CDCR approvals and Certificate of Confidentiality	1-6
Staffing & Training	
Select & train clinical and research staff	5-6
Set up offices at research sites	5-6
CM Implementation	
SATF subject recruitment, baseline interviews, enrollment randomization	7-32
Community subject recruitment, attendance randomization	8-33
22-week CM intervention	8-39
Follow-up, Data Analysis, & Report Writing	
18-month post-release follow-up interviews	26-51
18-month post-release records data	28-53
Post-implementation focus groups with clients/staff, manual revision	40-42
Submit reports to NIDA (annual progress & final report)	12, 24, 36, 48, 60
Data analysis, publication writing, writing of final report	8-60

TRAINING PROCEDURES

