Data will be collected from subjects at two main time points. The baseline interview will occur at or shortly after recruitment, that is, approximately seven days prior to release from the institution. The follow-up assessment will occur 12 months following release to parole. This assessment point will include interviews with all subjects who can be contacted and collection of treatment participation data from programs. In addition to measures of individual-level performance, the study will also collect data to enable an assessment of the system impact and cost implications of the intervention.

BASELINE INTERVIEW

Baseline interviews will be conducted at the prison substance abuse programs in private offices at SATF or in a private room at Walden House. The baseline assessment, administered within two week of recruitment into the study, will include information on demographic characteristics, criminal history, risk level, drug use history, treatment history, participation in prison treatment, psychological status, motivation, perceived coercion, and HIV/AIDS risk. Measures of other variables will be collected from standard instruments. Locator data to assist in later follow-up tracking will also be collected. See Table 4 for the list of instruments or measures and their assessment points.

FOLLOW-UP DATA COLLECTION: 12 MONTHS

For the 12-month assessment, interviewers will meet with participants at locations that are safe, ensure privacy, and minimize travel costs. If participants are incarcerated, they will be interviewed in jail or prison. If a face-to-face follow-up interview is not feasible (e.g., client located out of state), the interview will be conducted by telephone. At the interview, research staff will obtain information on recidivism and criminal activity, drug use, and psychosocial functioning (see Table 3). Records data on treatment participation and criminal justice involvement will also be obtained.

DATA SOURCES - RESEARCH DOCUMENTATION FORMS

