Aim 2 For parolees who enter community treatment, determine whether providing incentives for attendance results in greater retention in treatment.

H3. Participants in the Attendance Incentive group will have a longer length of time in treatment than will participants in the Attendance Information group.

Aim 3 For parolees who enter community treatment, determine whether providing an incentive increases the likelihood that clients will participate in HIV testing and counseling.

H4. Participants in the Attendance Incentive group will be more likely to agree to receive HIV testing and to participate in post-test counseling than will participants in the Attendance Comparison group.

Aim 4 Assess the long-term impact of the use of incentives on drug use, crime, and psychosocial outcomes at 12 months following the end of the six-month intervention.

H5. Participants in the Attendance Incentive group will be more likely to be abstinent than will participants in the Attendance Information group at the Month 12 assessment.

H6. Participants in the Attendance Incentive group will have a lower percentage of arrests and reincarcerations than will participants in the Attendance Information group at the Month 12 assessment.

H7. Participants in the Attendance Incentive group will have better psychosocial outcomes (employment, education, family relationships, psychological functioning, and HIV risk) than will participants in the Attendance Information group at the Month 12 assessment.

Aim 5 Assess the long-term impact of the use of incentives to promote treatment participation on HIV-risk behaviors at 12 months following the end of the six-month intervention.

H8. At the Month 12 assessment, participants in the Attendance Incentive group will report lower levels of injection drug use and engagement in HIV-risk sexual behaviors than will participants in the Attendance Comparison group.

H9. At the Month 12 assessment, participants in the Attendance Incentive group will report greater participation in HIV-related services (of any type) over the period since discharge from Walden House than will participants in the Attendance Comparison group.

Aim 6 Assess issues of acceptability, satisfaction, and sustainability of the use of incentives to increase enrollment and retention among staff and clients.

RQ1. Were clients and treatment staff who participated in the CM intervention accepting of and satisfied with the use of incentives to promote enrollment and attendance?

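### H9 measures HIV-service use from discharge, a date the incentive is meant to delay, so if H3 holds the two arms are compared over unequal periods

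*Protocol*

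**What the plan says.** H9 stands under Aim 5 in the Primary Aims section and is repeated under Expected Outcomes. It predicts that at the Month 12 assessment the Attendance Incentive group will report "greater participation in HIV-related services (of any type) over the period since discharge from Walden House".

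H3, under Aim 2, predicts: "Participants in the Attendance Incentive group will have a longer length of time in treatment than will participants in the Attendance Information group".

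The protocol gives three times for the follow-up interview:

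- Introduction to the Study and Specific Aims: "Twelve months after the end of the intervention (i.e., 17 months following release to parole), all study participants will be tracked".
- Assessment Points: "The follow-up assessment will occur 12 months following release to parole".
- Project Timeline, Table 3: "18-month post-release follow-up interviews".

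All three run from release or from the end of the intervention. The intervention period is fixed for each man and does not end at discharge: "You are in the study for 22 weeks from the day you start earning money" (What Constitutes Attendance, Discharge). The same paragraph allows re-admission after discharge, and H9 does not say which discharge starts its period.

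Hypothesis Testing plans t-tests and chi-square tests at first. Regression follows if covariates are needed for baseline differences, with possible extension to generalized linear models. It names no rate, offset or common start date for H9. Discharge dates are collected (Records Data).

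**The concern.** The start of H9's period is itself an outcome of the intervention. If the incentive keeps men in treatment longer, it moves their start date towards a closing date that does not move with it. At the same monthly rate of service use, the arm that stays longer would then report less. Intent-to-treat analysis does not help, because every randomized man can be included and still be observed over a different length of time. Adjustment for baseline imbalance does not help either, because time since discharge is not a baseline variable.

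Length is not the only problem. A service received on day 100 counts for a man who left on day 38 and does not count for a man still in the program.

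What is at stake is mainly power: a real benefit on H9 would be partly hidden, and more so the better the incentive works on retention.

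**Working it through.** **The plan's own figure.** The protocol gives no length for the H9 period. For the interview outcomes that include H9, Power Analysis states power of about .75 with d about 0.30 and about 170 men. At 85 per arm, two-sided .05: power = Φ(0.30 × √(85/2) − 1.96) = Φ(1.956 − 1.96) = 0.50. That gap is a separate matter. Here 0.50 serves only as the starting point.

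**Inputs from the protocol.** Without incentives, "the average length of attendance is 38 days" (Conception of the Problem). The intervention lasts 22 × 7 = 154 days. Interviews fall 12, 17 or 18 months after release, that is at about 365, 517 or 548 days. Power Analysis cites d = 0.34 for attendance and d = 0.49 for drug use; the second is borrowed here for retention.

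**Assumptions, because the protocol gives no figure.** The SD of stay is 40 to 60 days. Discharge is timed from release as if admission were immediate. Information-arm service use is 40%. Service use has the same constant rate in both arms.

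**Incentive-arm mean stay.** 38 + 0.34 × 40 = 51.6 days; 38 + 0.49 × 60 = 67.4 days. A doubling to 76 days is added as a generous upper case.

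**Period and reported use.** Period w = interview day − discharge day. With equal rates, the incentive-arm proportion is 1 − 0.60^(w_incentive / w_information).

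| Incentive-arm stay | 12 months (information arm 327 days) | 17 months (479 days) | 18 months (510 days) |
|---|---|---|---|
| 52 days | 314 (−4%), 38.7% | 466 (−3%), 39.1% | 496 (−3%), 39.2% |
| 67 days | 298 (−9%), 37.2% | 450 (−6%), 38.1% | 480 (−6%), 38.2% |
| 76 days | 289 (−12%), 36.3% | 441 (−8%), 37.5% | 472 (−7%), 37.7% |
| 154 days (one man against another) | 211 (−35%), 28.1% | 363 (−24%), 32.1% | 394 (−23%), 32.6% |

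The first three rows compare arm averages. They give a spurious deficit of about 1 to 4 percentage points against 40%. The last row contrasts two individual courses and is not an arm effect.

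**Chance of a significant result against the incentive when true rates are equal.** Φ(Δ/SE − 1.96), with 85 per arm. At 67 days and a 12-month interview, Δ = 0.028 and SE = 0.075, which gives about 6%. Across stays of 52 to 67 days the range is 3 to 6%. At 76 days with a 12-month interview it is Φ(0.037/0.0745 − 1.96), about 7%. The nominal figure is 2.5%.

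**Loss of power when there is a real benefit.** Take 40% against 54.9% over equal periods (h = 0.30, power 0.50). Shortening the incentive arm's period as for stays of 52 to 67 days, and using power = Φ(h√(85/2) − 1.96):

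- 17-month interview: h = 0.279 to 0.255, power 0.44 to 0.38.
- 12-month interview: h = 0.270 to 0.233, power 0.42 to 0.33.

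**With a common origin.** From 22 weeks after randomization to 12 months later, both arms have about 365 days. The ratio is 1.00, and equal rates give equal proportions.

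**The case against.** *The direction is not guaranteed.* This stands. A reader might infer that the bias always runs against H9. It does so only if H3 is true and service rates are roughly constant and similar. If stays do not differ, there is no average bias. If most uptake comes soon after discharge, the length of the period matters little. Time in custody may also differ between the arms, so calendar days are not equal opportunity.

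*The sizes rest on assumptions.* This also stands. The 38 days describes men referred from the SATF prison programs. The Attendance Phase also enrols others, including in-custody clients who cannot leave the premises unaccompanied. The SD of stay and the level of service use are not given.

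*The period contradicts Aim 5.* A reader might infer this, since Aim 5 looks at the impact "on HIV-risk behaviors at 12 months following the end of the five-month intervention". But that wording fixes when the assessment takes place, not the period it looks back over. There is no contradiction.

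*The discharge anchor has a purpose.* It keeps on-site testing, for which incentive-arm men receive a $10 voucher, out of H9; H4 tests that separately. The purpose is sound, but separate reporting of Walden House services serves it without an unequal period.

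*An offset could be left to the analysis plan.* In part. The follow-up item is not at hand, and H9 may be a yes/no question. But the protocol fixes the period in the hypothesis itself, in two places. An offset would repair the unequal length and still start the clock at a post-randomization date.

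**Conclusion.** The point holds in a limited form. As written, H9 compares the arms over periods that the intervention itself can shorten, and no stated test corrects this. Under H3 and similar, roughly constant service rates, the incentive arm's period is about 3 to 12% shorter on average. That is worth about 1 to 4 percentage points at an assumed 40% use, with power falling from 0.50 to between 0.33 and 0.44 for stays of 52 to 67 days.

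Two stronger readings are not supported. The 24 to 35% gaps belong to a pair of individual men, not to the arms. A significant false finding of harm is unlikely: about 3 to 7% in the cases worked, against a nominal 2.5%. The main risk is that a real benefit is diluted. H9 is a secondary outcome, and the primary outcomes of admission and retention are not affected.

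**What to change.** 1. Reconcile the three interview times first. A window from week 22 to 12 months later ends 154 + 365 = 519 days after the attendance randomization, which itself follows release. An interview 17 months (517 days) after release would fall just short, and one at 12 months far short. Schedule the interview at or after the end of the window, timed from randomization.
2. Define H9 over a fixed calendar window with one origin, the attendance randomization date, in both arms: for example from 22 weeks after randomization to 12 months later, whatever the discharge date. Do not anchor it to the first earning day, because information-arm men have none.
3. Report services received at Walden House separately from those received elsewhere, so that incentive-paid testing under H4 is not mixed in. Some overlap remains, since retention is measured up to 180 days: 180 − 154 = 26 days of the window.
4. Reword H9 in Primary Aims and in Expected Outcomes, and match the follow-up item to it.

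The cost is one hypothesis reworded in two places, a check of one interview item, and a settled interview date. The loss is that services used between an early discharge and week 22 no longer count. They can be described separately.
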